## SYNOPSIS

### TITLE OF TRIAL

A placebo controlled, double-blind, randomised trial investigating safety, tolerability, pharmacodynamics, and pharmacokinetics after intravenous administration of FE 204205 in patients with cirrhotic portal hypertension

### TRIAL SITE(S)

University of Barcelona, Hospital Clínic, Spain.

PLANNED TRIAL PERIOD	CLINICAL PHASE
First patient first visit: Q4 2016	1b
Last patient last visit: Q1 2018	

### BACKGROUND AND SCIENTIFIC JUSTIFICATION FOR CONDUCTING THE TRIAL

Complications of portal hypertension, including ascites, hepatorenal syndrome, and variceal bleeding, are leading causes of morbidity and mortality in cirrhosis. Cirrhosis is a common cause of death in adults worldwide. It results in approximately one million deaths per year worldwide, 170 000 per year in Europe, and 35 000 per year in the USA. Cirrhosis is the main indication for 5500 liver transplants each year in Europe.

Patients suffering from cirrhotic portal hypertension have an abnormally high splanchnic blood flow due to increased hepatic resistance and splanchnic arterial vasodilation. These circulatory disturbances cause a decrease in the effective arterial blood volume and a compensatory activation of the sympathetic nervous system, the renin-angiotensin-aldosterone system, and the non-osmotic release of vasopressin, which in turn results in fluid retention and renal vasoconstriction.

Terlipressin, a full V1A receptor agonist, has been shown to be effective in the management of several complications to cirrhotic portal hypertension. Terlipressin reduces the portal pressure and this effect is mediated by an arteriolar vasoconstriction in the splanchnic area. By counter-acting the splanchnic arterial vasodilation and increasing the effective arterial blood volume, thereby improving renal perfusion and glomerular filtration rates, terlipressin has been shown to improve renal function in patients with hepatorenal syndrome. There are also reports showing that terlipressin, by normalising the underlying circulatory derangements, is effective in the treatment of refractory ascites. The rationale for use of terlipressin for treatment of variceal bleeding is to produce splanchnic vasoconstriction and thereby reduce portal blood inflow and portal pressure,

thus decreasing portal-variceal flow and pressure.

Existing  $V_{1A}$  receptor agonists, such as terlipressin, are full agonists and may produce excessive vasoconstriction if not dosed carefully. The risk profile of  $V_{1A}$  full agonists requires careful titration and monitoring to prevent the development of serious adverse events (SAEs) due to tissue hypoxia and ischemia. Thus, the major limitation of existing agents is a risk of excess vasoconstriction, restricting their use to short term applications in inpatient settings under close monitoring by specialists.

FE 204205 is a novel, selective vasopressin 1a receptor ( $V_{1A}$ ) partial agonist in clinical development intended for the treatment of complications to cirrhotic portal hypertension. In comparison to full  $V_{1A}$  receptor agonists, the  $V_{1A}$  partial agonist FE 204205 is expected to have a substantially improved therapeutic index due to a lower maximal effect and lower risk for excessive vasoconstriction. In animal studies FE 204205 shows only approximately half of the maximal vasoconstriction produced by full agonists without any concomitant signs of ischemia (i.e. no increased lactate levels), which is assumed to result in adequate clinical vasoconstriction concomitant with the required safety.

Results from two Phase I studies, in which healthy subjects received FE 204205 intravenously, indicate that the maximal effect on vasoconstriction, by means of blood pressure, is reached at a plasma concentration of approximately 1 ng/ml, achieved by an intravenous infusion of 0.1 mg over 6 hours. The effect of the  $V_{1A}$  partial agonist FE 204205 appears to be capped compared to a full  $V_{1A}$  agonist, since increasing the dose 9-fold (from 0.1 mg to 0.9 mg over 6 hours) did not result in greater pharmacodynamic effects. Administration of 0.9 mg over 6 hours was well tolerated with an adverse events (AEs) profile related to the pharmacological effects of a  $V_{1A}$  receptor agonist.

Subcutaneous administration of FE 204205 resulted in the generation of an active metabolite (M1), characterised as a  $V_{1A}$  full agonist, at equimolar concentrations to FE 204205. The subcutaneous administration caused more AEs and of higher intensity than intravenous administration, and the maximal tolerated subcutaneous dose of FE 204205 was defined as 0.1 mg. After intravenous administration the M1 metabolite was detected only at very low concentrations,  $\leq 2\%$  of the FE 204205 concentration, and is not expected to show any appreciable pharmacodynamic effects in this trial.

This is the first study with FE 204205 in patients with cirrhotic portal hypertension and the selected endpoints will focus on the evaluation of safety and tolerability of the treatment in general, the investigation of effects on portal and systemic haemodynamics, and the pharmacokinetics of FE 204205.

## OBJECTIVES

- Safety and tolerability of single intravenous infusions of FE 204205
- Pharmacological effect of FE 204205 on systemic and portal haemodynamics in patients with cirrhotic portal hypertension
- Pharmacokinetics of FE 204205 after intravenous infusion
- Relationship between pharmacokinetics and pharmacodynamics of FE 204205
- Metabolites of FE 204205 in plasma and urine of patients
- Exploratory assessment of effects of FE 204205 on soluble biomarkers and renal function variables

## ENDPOINTS

[figure not shown]
- Type, frequency and intensity of adverse events (AEs)
- Electrocardiogram (ECG) (intervals, rhythm, and morphology)
- Clinical chemistry, haematology and urinalysis
- Venous blood gases including lactate
- Systemic haemodynamics: Blood pressures and heart rate by non-invasive measurements, pulmonary capillary wedge pressure (PCWP), pulmonary artery pressure (PAP), right atrial pressure (RAP), mean arterial pressure (MAP), and cardiac output (CO) by pulmonary artery catheterization. CO, MAP, and RAP will be used for calculation of the systemic vascular resistance (SVR)
- Portal haemodynamics by hepatic vein catheterization: Free hepatic venous pressure (FHVP), wedged hepatic venous pressure (WHVP), and inferior vena cava pressure (IVC). WHVP and the FHVP will be used for calculation of the hepatic venous pressure gradient (HVPG)
- Pharmacokinetics FE 204205: AUC, AUCt, %extrap AUC, Cmax, tmax, CL, Vz, t1/2, MRT, Ae, and CLR
- Metabolites in plasma and urine
- Blood and urinary biomarkers: Renin, aldosterone, norepinephrine, atrial natriuretic peptide (ANP), brain natriuretic peptide (BNP), urine creatinine, urine sodium, and urine osmolality

## METHODOLOGY

This is a trial investigating the safety, tolerability, pharmacokinetics, and pharmacodynamics of FE 204205 in cirrhotic patients with portal hypertension and anticipated HVPG  $\geq$  12 mmHg. The trial is divided in two parts:

[figure not shown]
**Part 1** is an open-label investigation of safety, tolerability, pharmacokinetics and pharmacodynamics of increasing intravenous doses of FE 204205 and will include 6 patients. The first two patients will receive their respective first dose on separate days. Systemic and portal haemodynamics will be assessed by pulmonary artery and hepatic vein catheterization on Day 3. Each patient will receive three ascending doses of FE 204205, given once daily as 2-hour infusions on three consecutive days. Dose escalation on Days 2 and 3 will only commence provided that the increase in mean arterial pressure from baseline is <15 mmHg, absolute mean arterial pressure ≤120 mmHg, systolic blood pressure ≤160 mmHg, diastolic blood pressure ≤100 mmHg, and heart rate ≥55 beats per minute at any of the vital signs assessments during the 4 hours after start of infusion on the previous day. If these criteria are not met, the same dose will be administered the next day. If the increase of dose results in non-tolerable effects, the preceding tolerated dose will be reverted to for the remaining administrations in that patient.

For the first 3 patients, the initial treatment given on Day 1 will be a single dose of 0.01 mg FE 204205 followed by planned doses of 0.025 mg FE 204205 on Day 2 and 0.05 mg FE 204205 on Day 3. For the remaining 3 patients, the planned single doses are 0.025 mg FE 204205 on Day 1, 0.05 mg FE 204205 on Day 2 and 0.1 mg FE 204205 on Day 3. After the first 3 patients have completed all Visit 2 assessments, a Safety Review Committee (SRC) with at least one external expert will evaluate the safety, tolerability, and pharmacodynamics of the compound and will decide if the dosing regimen can be increased as planned, or if a modified (lower) dose regimen should be applied.

A Safety Review Committee (SRC) with at least one external expert, will evaluate the safety, tolerability, and pharmacodynamics of the compound after the completion of Part 1 to recommend what dose of FE 204205 to evaluate in part 2.

**Part 2** is a placebo controlled, double-blind, randomised investigation evaluating the effects of a single dose of FE 204205 on portal haemodynamics and will include 16 patients receiving FE 204205 and 4 patients receiving placebo. Each patient will receive a 2-hour intravenous infusion of the maximum tolerated dose of FE 204205 as defined in Part 1, or placebo, on Day 1. Systemic and portal haemodynamics will be assessed by pulmonary artery and hepatic vein catheterization.

## NUMBER OF SUBJECTS

### Part 1

6 patients. Subjects withdrawn prematurely in Part 1 will be replaced in order to achieve 6 subjects that complete all Visit 2-assessments.

### Part 2

Approx. 20 patients in Part 2. At least 18 patients in Part 2 with HVPG  $\geq 12$  mmHg. Measures will be taken to reach a balanced ratio between genders (i.e. at least 1/4 of each gender) in the study.

## CRITERIA FOR INCLUSION / EXCLUSION

Patients, 18-65 years of age, with cirrhotic portal hypertension and anticipated HVPG  $\geq 12$  mmHg

### Inclusion criteria

1. Signed written informed consent
2. Male or female patient, 18-65 years of age with confirmed evidence of cirrhosis
3. From medical history anticipated HVPG  $\geq 12$  mmHg
4. Negative pregnancy test at Screening and on Day -1
5. Agrees to use an adequate method of contraception during the study until the follow-up visit, if not abstinent. Adequate methods of contraception include condom with or without spermicidal gel (adequate only for male participants), intrauterine device, surgical sterilisation, vasectomy, oral contraceptive pill associated with inhibition of ovulation, depot progesterone injections
6. Negative urine drug screen and alcohol urine test at Screening and on Day -1

### Exclusion criteria

1. Patients with co-existing disease including but not restricted to significant organ failure, decompensated cirrhosis with a Child Pugh score  $> 12$  or requirement for organ support, and acute pancreatitis
2. Type 1 hepatorenal syndrome
3. Severe hyponatremia (serum sodium concentration  $< 125$  mEq/L)
4. Acute-on-chronic liver failure
5. Hepatic encephalopathy  $\geq$  grade 2

6. Hepatocellular carcinoma outside the Milan criteria (<5 cm for a single lesion or less than 3 lesions with the largest measuring  $\leq 3$  cm)
7. Bacterial infection within 7 days prior to dosing
8. Gastrointestinal bleeding within 6 weeks prior to dosing.
9. Severe renal impairment i.e. estimated creatinine clearance  $< 30$  mL/min calculated according to the The Modification of Diet in Renal Disease (MDRD) study equation
  
10. History of underlying chronic heart disease, including but not restricted to heart failure NYHA class III or IV, angina pectoris, or myocardial infarction
11. Diagnosed ongoing hypertension
12. Symptomatic peripheral vascular disease including Raynaud's syndrome
13. Diagnosed chronic obstructive pulmonary disease (COPD)
14. Severe grade 3 anemia, i.e. Hb  $< 8.0$  g/dL ( $< 4.9$  mmol/L)
15. Use of vasopressin or terlipressin within 7 days prior to dosing
16. Permanent use of beta-blocker or a long-acting so called nitro-dilator, or if temporary use within 7 days prior to dosing
17. Use of treatments for hepatitis B or C virus within 6 months of randomisation or anticipated use during the trial period
18. Positive serology for human immunodeficiency virus (HIV)-1 or HIV-2
19. Women being pregnant or breastfeeding at screening and Day -1
20. Hypersensitivity towards any component of FE 204205 formulation
21. Sensitivity to contrast media
22. Intake of an investigational medicinal product within the last 8 weeks preceding screening or longer if judged by the investigator to possibly influence the outcome of the current study
23. Body mass index (BMI)  $< 18$  or  $> 35$  kg/m^2
24. Abuse of alcohol or drugs within 6 months prior to screening
25. Mental incapacity or language barrier precluding adequate understanding or co-operation
26. Previously included in this trial
27. Considered by the investigator to be unsuitable to participate in the study for any other reason

## **MEDICINAL PRODUCTS**

### Investigational medicinal products (IMP)

FE 204205: 10 mg/mL in 10 mM acetate buffer, pH 4.5, with mannitol to isotonicity

Placebo: Sodium chloride 0.9%

### Non-investigational medicinal products (non-IMP)

Sodium chloride 0.9% for dilution of IMP  
Midazolam  
Mepivacaine  
Iodine

## DURATION OF TREATMENT

In part 1, each patient will receive three ascending doses of FE 204205, given once daily as 2-hour infusions on three consecutive days. In part 2, each patient will receive a single 2-hour intravenous infusion of FE 204205 or placebo.

## TRIAL PROCEDURES / ASSESSMENTS

### Part 1:

Before inclusion into the study, all patients will undergo a general physical examination, including vital signs, ECG and laboratory assessments including haematology, clinical chemistry, and urinalysis.

Patients will come for a residential stay, lasting between Day -1 to Day 4. Each patient will receive three ascending doses of FE 204205, given as 2-hour infusions over three consecutive days. During the treatment period, adverse events, vital signs, ECG, body weight, and clinical laboratory parameters will be assessed. Blood samples for measurement of biomarkers and plasma concentrations of FE 204205 and metabolites will be collected at specified time-points. Urine collection will be performed at specified timepoints for analysis of urinary output, urinary biomarkers and excretion of FE 204205 and metabolites. Patients will be confined to the clinic during the treatment period and will be carefully monitored for adverse events and effects on systemic haemodynamics. Systemic and portal haemodynamics will be assessed by pulmonary artery and hepatic vein catheterization with measurements performed before, during, and immediately after the intravenous infusion on Day 3. Catheterization of the hepatic vein and the pulmonary artery is a moderately invasive technique and will be carried out under mild sedation with midazolam and local anaesthesia.

HVPG will be the primary pharmacodynamic parameter and assessments will be performed pre-dose, and at 1 and 2 hours after start of the intravenous administration. HVPG is the golden standard for evaluation of portal hypertension in patients with cirrhosis. A balloon-tipped catheter is placed in the right or middle hepatic vein and the FHVP and WHVP are measured, the latter is when the vein is occluded by the balloon. All measurements will be performed at least in duplicate (the average will be used for the endpoint), and permanent tracings will be obtained with a multichannel recorder and adequately calibrated transducers. The HVPG is calculated as the difference between the WHVP and the FHVP. Hepatic vein catheterization is a safe procedure and is used routinely in clinical practice in patients with chronic liver disease. In association with the hepatic vein catheterization, inferior vena cava pressure (IVC) will be measured pre-dose and at 2 hours after start of the intravenous administration.

Immediately before and after the hepatic vein catheterization (i.e. pre-dose and at 2 hours after start of the intravenous administration) a Swan-Ganz catheter will be introduced into the pulmonary artery for measurements of systemic haemodynamics (pulmonary capillary wedge pressure [PCWP], pulmonary artery pressure [PAP], right atrial pressure [RAP], mean arterial pressure [MAP], and cardiac output [CO]). CO, MAP, and RAP will be used for calculation of the systemic vascular resistance [SVR].

A follow-up visit will be performed between Day 7 and Day 14.

**Part 2:**

Before inclusion into the study, all patients will undergo a general physical examination, including vital signs, ECG and laboratory assessments including haematology, clinical chemistry, and urinalysis.

Patients will come for a residential stay, lasting between Day -1 to Day 2. Each patient will receive a 2-hour intravenous infusion of FE 204205 or placebo on Day 1. During the treatment period, adverse events, vital signs, ECG, body weight, and clinical laboratory parameters will be assessed. Blood samples for measurement of biomarkers and plasma concentrations of FE 204205 and metabolites will be collected at specified time-points. Urine collection will be performed at specified timepoints for analysis of urinary output, urinary biomarkers and excretion of FE 204205 and metabolites.

On Day 1, systemic and portal haemodynamics will be assessed by pulmonary artery and hepatic vein catheterization.

A follow-up visit will be performed between Day 5 and Day 12.

**STATISTICAL METHODS**

**Power**

Part 1: No formal sample size calculation has been made. However, the number of patients (6) is considered sufficient to provide adequate information about the safety and tolerability of FE 204205, and thus inform about the suitable dose to evaluate in part 2.

Part 2: Since this is a first exploratory evaluation of the efficacy of FE 204205 on reducing portal pressure, the sample size and power calculations were performed by evaluation of the intra-group difference (before and after treatment with FE 204205). Assuming, based on the literature, a standard deviation (SD) of relative change from baseline of 12 %, a sample size of 14 patients on active treatment was deemed sufficient to detect a within-group 10 % reduction in HVPG, with  $\alpha = 0.05$  and  $1-\beta = 0.8$ . Taking into consideration that it occasionally can be technically challenging to assess HVPG, a total of approx. 20 patients (16 on FE 204205 and 4 on placebo) are targeted (4:1 randomisation).

## Statistical analyses

The statistical analysis will include descriptive statistics reflecting the explorative nature of the study. In general, the data will be presented by dose level in Part 1 and by treatment group in Part 2.

No single primary endpoint has been identified, and there will be no multiplicity adjustments for the statistical analysis comparisons performed. In Part 2, the statistical analyses are based on the assumption that a placebo effect is negligible, so the primary statistical analyses will be performed using analyses of covariance of the change and relative change from baseline in the pharmacodynamic parameters adjusting for the respective baseline values to assess the significance of comparisons with baseline within each group (in the treatment group to assess the treatment effect and in the placebo group to assess the assumption of a negligible placebo effect). Secondary inferential statistics will be computed between placebo and active treatment using an analyses of covariance with treatment group as an additional factor.

The pharmacodynamic and safety endpoints will be analysed for the safety analysis set. The PK analyses will be performed for the PP analysis set.

HVPG will be derived as the average of the duplicate assessments, separately calculated for each scheduled assessment, of the difference between WHVP and FHVP (WHVP- FHVP).

HVPG and other haemodynamic variables will be assessed as change from baseline to 1 and 2 hours post dose separately analysed for each treatment group, and compared between groups.

Non-compartmental pharmacokinetic analysis of FE 204205 will be performed.

Changes in safety parameters will be evaluated by subject listings and descriptive statistics.

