### 9.1 Determination of Sample Size

Part 1: No formal sample size calculation has been made. However, the number of patients (six) is considered sufficient to provide adequate information about the safety and tolerability of FE 204205, and thus inform about the suitable dose to evaluate in part 2.

Part 2: Since this is the first exploratory evaluation of the efficacy of FE 204205 on reducing portal pressure, the sample size and power calculations were performed by evaluation of the intra-group difference (before and after treatment with FE 204205). Assuming, based on the literature, a standard deviation (SD) of relative change from baseline of 12 % (see table below), a sample size of 14 patients on active treatment was deemed sufficient to detect a within-group 10 % reduction in HVPG, with  $\alpha = 0.05$  and  $1-\beta = 0.8$ . Taking into consideration that it occasionally can be technically challenging to assess HVPG, a total of 20 patients (16 on FE 204205 and 4 on placebo) are targeted (4:1 randomisation).

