**Table 9-1 SD of relative (%) and absolute change from baseline in HVPG**

Reference	Inv Drug	SDs of %Change in HVPG	SDs of Change in HVPG (mmHg)
Escorsell et al. (7)	Terlipressin	9%, 12%	
Abraldes et al. (8)	Simvastatin	9%, 12%	
Berzigotti et al. (9)	NCX-1000	(~13 %)	2.2 mmHg* (baseline 17.1 mmHg)
Reverter et al. (10)	Saproterin	(~14 %)	2.2 mmHg* (baseline 16.0 mmHg)

\*derived from reported mean change, sample size and p-value (two-sided paired t)

A reasonable estimate of the SD would be 12% (also assumed by Reverter et al. (10) in their power calculations)

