### 9.6.1 General Considerations

All endpoints (see Section 9.6.2) will be analysed using descriptive statistics. In general, the data will be presented by dose level and time point in part 1 and by treatment group and time point in Part 2.

Inferential analyses on change and relative change from baseline in systemic and portal haemodynamic variables from Part 2 of the study will be conducted by using an Analyses of Covariance (ANCOVA) adjusting for the respective baseline value per treatment arm and time point. The focussing on mean change from baseline is based on the assumption the of a negligible placebo effect as reported in e.g. (7,8). Nevertheless, placebo-subtracted treatment effects will also be inferred (despite of limited power) using ANCOVA with treatment group as an additional factor.

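### The primary Part 2 analysis tests each arm's mean change with a per-arm ANCOVA on baseline; in the active arm this is modestly anti-conservative, and it is not the test behind n = 14.

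*Combined protocol and SAP*

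**What the plan says.** The Statistical analyses part of the synopsis calls the within-group ANCOVA of change and relative change primary, with the model "adjusting for the respective baseline values to assess the significance of comparisons with baseline within each group". The active arm's result is to show the treatment effect. The placebo arm's result is to check that a placebo effect is negligible.

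Section 9.6.1 repeats the model, "adjusting for the respective baseline value per treatment arm and time point", and names the target: "The focussing on mean change from baseline is based on the assumption" that the placebo effect is negligible. The comparison of arms comes second: "Secondary inferential statistics will be computed between placebo and active treatment using an analyses of covariance with treatment group as an additional factor".

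Section 9.1 sizes the trial differently: "the sample size and power calculations were performed by evaluation of the intra-group difference (before and after treatment with FE 204205"), and "a sample size of 14 patients on active treatment was deemed sufficient to detect a within-group 10 % reduction in HVPG".

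Neither section says at which baseline value the within-arm mean is estimated or how its standard error is formed. Section 9 leaves detail to a separate Statistical Analysis Plan.

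**The concern.** Baseline adjustment helps when two arms are compared, because it removes chance imbalance and residual noise from the difference. Within one arm there is nothing to balance. At the arm's mean baseline the fitted mean equals the raw mean change, so the adjustment alters only the error term.

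Change contains the baseline reading with a minus sign, so noise in that reading makes change and baseline negatively correlated even without a drug effect. The regression takes this shared variation out of the residual, but it is still part of the sampling error of the mean change.

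At stake are the p-values from which the plan reads the drug effect on HVPG and the other haemodynamic variables, and the only check of the assumption that justifies reading the effect within one arm.

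**Working it through.** **Reproducing the plan's figure.** Inputs from section 9.1 and Table 9-1: 10% fall, SD 12%, alpha 0.05, power 0.8. For a two-sided one-sample (paired) t-test the noncentrality is (10/12)·√n. Power is 78.8% at n = 13, 82.2% at n = 14 and 87.6% at n = 16. So n = 14 is right for the paired t-test. The plan does not say whether alpha is two-sided; a one-sided t-test would need 11 or fewer.

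**The standard error.** Let D be change, B baseline and r their correlation. Fit D = a + g·(B − mean B) + error in one arm.

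- Estimate: a = mean of D, the same as without the covariate.
- Squared standard error from the model: estimates σ_D²(1 − r²)/n.
- Actual sampling variance of the mean change: σ_D²/n.
- Omitted: r²σ_D²/n, which equals g²·Var(B)/n.

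With n − 2 degrees of freedom, and no true change, the real two-sided level is P(|T| > t(0.975; n−2)·√(1 − r²)). It equals 5% only if r = 0.

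**The size of r.** With no effect and equal variances at both readings, Cov(B, D) = −σ_D²/2, so r = −σ_D/(2σ_B). Table 9-1 gives σ_D = 2.2 mmHg in two studies, for example "2.2 mmHg* (baseline 17.1 mmHg"). The documents give no baseline SD, so σ_B is an assumption, taken from 2.5 to 5 mmHg.

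**Active arm, n = 16, t(0.975; 14) = 2.145, absolute change.**

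| Baseline SD (mmHg) | r | √(1 − r²) | 2.145 × √(1 − r²) | Two-sided level |
|---|---|---|---|---|
| 5 | −0.22 | 0.976 | 2.09 | 5.5% |
| 4 | −0.275 | 0.961 | 2.06 | 5.8% |
| 3 | −0.367 | 0.930 | 2.00 | 6.6% |
| 2.5 | −0.44 | 0.898 | 1.93 | 7.5% |

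Simulation with at least 100,000 trials per case agrees. False claims of a reduction run from 2.8% to 3.7%, against a nominal 2.5%.

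**Relative change.** This was simulated with mean baseline 16.5 mmHg, which lies between the 16.0 and 17.1 mmHg of Table 9-1. The two-sided level is about 7% to 8.5% across the same baseline SDs. False claims of a reduction are about 1.8% to 2.3%. The excess lies toward an increase: with no absolute change, the mean percentage change is itself about +1%, because noise in the baseline also sits in the denominator. The paired t-test gives about 4.6-5.2% over both scales.

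**Interval width, active arm.** The paired interval divided by the ANCOVA interval is about (2.131/2.145)/√(1 − r²), with a negligible small-sample term: 1.02 at baseline SD 5 and 1.11 at 2.5. Relative change reaches about 1.12.

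**Placebo arm, n = 4.** The t quantile rises from 3.18 (3 df) to 4.30 (2 df), a factor of 1.35. The expected residual SD on 2 df is smaller by 0.886/0.921 = 0.962, so the product is 1.30. Multiplying by √(1 − r²) gives 1.27 at baseline SD 5 and 1.17 at 2.5. For relative change with a baseline SD as low as 2.2 mmHg it falls to about 1.10. So these intervals are wider on average, by about 10-27%, with the same estimate. They do not cover better: by the formula above, the level for absolute change is still 5.2-6.1%.

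**The case against.** The strongest reply is that the plan does not fix the evaluation point. If the uncentred intercept were tested, its standard error would be about 3.6 to 8 times larger, the opposite direction. This stands, and the finding is conditional on evaluation at the arm's mean baseline. But the intercept is the change at an HVPG of zero, which is not the mean change named in section 9.6.1, so that reading does not rescue the plan.

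Second, given the observed baselines, the test holds its level for the mean change at that mean baseline. This is true. It answers a narrower question than the population mean change on which section 9.1 sized the trial.

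Third, the trial is exploratory, with no single primary endpoint and no multiplicity adjustment. Many variables, two scales and two time points are tested, which matters more for overall error than a few points on one test. This stands and limits the importance. It does not justify a standard error that is wrong for its target when the right one costs almost nothing.

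Fourth, readings are at least duplicate and averaged, which reduces measurement noise. The calculation starts from the SD of change in the plan's own table, and the true baseline SD could put the effect at the low end of the range.

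Fifth, the FE 204205 against placebo ANCOVA, where baseline adjustment is valid, is already planned. It is secondary, and the plan concedes its limited power.

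**Conclusion.** The point holds for the active arm and is modest. With the mean taken at the arm's own mean baseline, 16 patients, an SD of change of 2.2 mmHg and a baseline SD assumed between 2.5 and 5 mmHg, the two-sided level is about 5.5-7.5% for absolute and about 7-8.5% for relative HVPG change. The primary test also differs from the paired t-test that yields n = 14. In the placebo arm the model weakens the check of a negligible placebo effect.

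A reader might infer more than the documents support:

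- That the standard error is too small in every case. This needs a non-zero correlation of change with baseline and an evaluation point the plan leaves open.
- That the trial breaks a promised 5% level or reports intervals that are too narrow. Alpha 0.05 appears only as a planning value, and no confidence intervals are announced.
- That intervals are too short in both arms. In the placebo arm they are wider than paired intervals.
- That false claims of benefit are inflated on the powered scale. For relative change, false reductions stay at or below 2.5%.
- That noisier haemodynamic variables fare much worse. The documents give no correlations from which to put a figure on that.

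**What to change.** In the synopsis (Statistical analyses) and section 9.6.1, test and estimate the within-arm change and relative change at each time point with a one-sample (paired) t-test and its 95% confidence interval. Keep ANCOVA with baseline as covariate only for the FE 204205 minus placebo contrast.

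The cost is wording: no new data and no change to the sample size, which already rests on this test. Active-arm intervals become roughly 2-12% wider, and placebo-arm intervals become narrower on average.
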